Objective 3: We will examine the impact that the intervention has on attendance at scheduled dental treatment appointments over the next 12 months.

Secondary Objectives:

We will examine whether I-CBT has similar effects on related measures (pain sensitivity, anxiety sensitivity, distress tolerance, symptoms of specific phobia of dental procedures, blood-injury-injection phobia, sleep disturbance and sleep-related impairment, functional impairment due to dental anxiety, and consumer satisfaction) at one- and three-month follow-ups.

We will also examine whether the Internet-based intervention reduces anticipated and perceived pain and anxiety during dental procedures in immediately pursuant appointments for dental treatment.

We will also examine whether baseline levels of distress tolerance and pain sensitivity moderate the efficacy of the dental anxiety intervention.

5) Rationale and Significance

Page 2 of 28 Revision: May 12, 2023

Dental anxiety (i.e., anxiety related to undergoing dental procedures) is a major public health concern, as it leads to underutilization of dental care and poor oral health. Approximately 10-20% of individuals in the US endorse significant dental anxiety, and 10-50% cancel regular dental care appointments or delay treatment for a painful dental condition due to fears of dental procedures (Sohn & Ismail, 2005). Patients with dental anxiety are more likely to be referred for nitrous oxide sedation (Boyle, Newton, & Milgrom, 2009) and use emergency dental services (Kanegane, Penha, Borsatti, & Rocha, 2003), both of which increase individual and public dental healthcare costs. Dental anxiety has been consistently associated with increased oral health problems and impairment (e.g., more cavities; Armfield, Stewart, & Spencer, 2007). Few studies have examined the efficacy of psychological treatments for dental anxiety (Gordon, [name], Tellez, & Ismail, 2013), and most of the existing empirically supported psychological interventions cannot be easily disseminated within dental healthcare settings, as they must be administered by highly trained clinicians over a number of sessions. Therefore, it is the goal of our ongoing research program to develop a brief online therapy for dental anxiety that could be easily implemented in dental clinics, allowing for broader dissemination.

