If the potential patient responds that they would not be interested, the interviewer will thank the patient for his/her time and terminate the call. If the patient responds affirmatively (i.e., gives verbal consent for the brief screening), the interviewer will first ask one screening question (age) and then administer the Modified Dental Anxiety Scale (Humphris et al., 1995), which is the primary screening measure of dental anxiety employed in this study (see attached measures file for specific questions). The interviewer will also ask whether the patient experiences impairment as a result of dental anxiety. If the patient fails to meet these screening criteria or appears to be insufficiently fluent in English, the interviewer will thank the patient for his/her time and terminate the call. If the patient meets criteria for dental anxiety and impairment, the interviewer will then administer the Medical Screening Interview, and if the patient meets any exclusion criterion based on that interview, the call will be similarly terminated. If not, the interviewer will provide more extensive information about the study and the risks and benefits of study participation (see attached "Summary Consent Script to be Read During Screening Phone Call"), and verbal consent for full study participation will be obtained. If the patient is still willing and appears to meet inclusion/exclusion criteria as outlined above, he/she will be scheduled for a second ("pre-intervention" or "baseline") interview and questionnaire administration. Patients will be randomized to one of three arms as described above.

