administer the Medical Screening Interview, and if the patient meets any of the exclusion criteria based on that interview, the call will be similarly terminated. If not, the interviewer will provide more extensive information about the study and the risks and benefits of study participation (see attached "Summary Consent Script to be Read During Screening Phone Call"), and verbal consent for full study participation will be obtained. If the patient remains interested, he/she will then be offered the opportunity to schedule an appointment for the pre-intervention assessment session. Note that recruitment will be expanded to include the TUKSoD Graduate Clinics [Endodontology, Periodontology, Advanced Education General Dentistry] if needed to achieve enrollment milestones.

Enrollment/Baseline (Time 1)

The interviewer will administer the specific phobia module of the Anxiety and Related Disorders Interview Schedule for DSM-5 (ADIS-5) - Adult Version (Brown & Barlow, 2014). Questionnaires specified in Table 1 (Measures and Timing of Their Administration) will also be administered by the interviewer over the phone. Alternatively, for those patients with Internet access and who prefer to use it, the questionnaires can be completed online through the use of an online data collection service.

Senior research staff will administer the randomization of participants (computer generated). The file will be secured and restricted to the time of randomization. Randomization will be done after the patient has received the consent summary, all baseline assessments are completed, and there are no further concerns about exclusion criteria. At that time, the study coordinator will be instructed to make an appointment for the Clinic Visit (Time 2), but the patient's randomization condition will not be revealed until the patient has arrived at the clinic and in-person informed consent procedures are completed.

Intermediate Visits (Times 2 and 3)

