Modified Dental Anxiety Scale (MDAS; Humphris et al., 1995). The MDAS is a widely used 5-item measure assessing fear of dental procedures, including cleaning, drilling, and local anesthetic injections; for example, "If you were about to have your tooth drilled, how would you feel?" Items are rated on a 5-point Likert-type scale ranging from 1 (not anxious) to 5 (extremely anxious). The total score ranges from 5 to 25; a score of 19 or above indicates high anxiety based on receiver operating characteristic analyses from two studies. The MDAS has demonstrated good internal consistency (α = .89 in Humphries et al., 1995; α = .91 in our pilot work) and test-retest reliability (r = .82). The MDAS will be administered at several occasions throughout the study. We will also briefly contact patients and ask them to complete the MDAS by phone or online at 6-month and 12-month follow-ups as well.

Medical Screening Interview. During the initial telephone screening, we will administer a medical screening interview that has been used in previous research by former PI [name] at Temple University. This medical screening interview assesses a number of medical conditions that may make it inadvisable for the potential participant to be exposed to anxiety-evoking materials unless well-controlled. If the potential participant meets criteria for any of these medical conditions and does not report that they are controlled by medication or other appropriate means, that potential participant will be excluded. It is also important to note that the Faculty Practice Clinic (the clinic in which the trial will be conducted) also conducts it own medical screening and will not schedule a patient for an appointment for dental care if the patient scores positive for any of the listed conditions on their form unless it is medically controlled (patient will be first referred out for appropriate medical care before coming back to the dental clinic when the medical condition is controlled). Although the routine clinical procedures of Faculty Practice Clinic are not a formal part of our protocol, they are thorough and suggest that our procedures are conservative, as we are recruiting only from the population of patients for whom an appointment for dental care has already been scheduled.

Other Self-Report Questionnaires

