We propose general statistical analyses and sample size considerations for the U01 trial. Initial analyses will be conducted to determine normality of distributions of the continuous variables, and any necessary transformations will be conducted. Primary outcomes will be the MDAS (score ranging from 5 to 25) and the rating of fear of dental procedures from the ADIS-5 (0=no fear to 8=very severe fear). All eligible patients will be randomly assigned to one of the three conditions described above. Although randomization should provide relatively comparable groups, demographic variables that differ between groups and are correlated with the primary outcomes will be used as covariates. Patients will receive a full battery assessment of outcome measures at baseline and 1 and 3 months after the day of their index dental appointment (as well as assessments on the day of their index dental appointment).

Page 16 of 28 Revision: May 12, 2023

Preliminary statistical analysis will include measures of central tendency and dispersion, as well as an examination of the bivariate relationships among the primary and secondary outcome variables (e.g., client satisfaction, blood-injury-injection phobia), potential moderators (e.g., distress tolerance and pain sensitivity), and demographic characteristics.

Differences between the groups on baseline demographic, clinical and psychological measures will be examined using χ^2 (Pearson) or Student's *t*-tests, as appropriate. Moreover, differences on the variables listed above among completers and drop-outs will also be explored. Both per protocol and intention to treat (ITT) analyses will then be conducted.

Specific Aim 1

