injury-injection phobia). Statistical significance will be set at p < .05. MI will be used to handle missing follow-up data as described below.

Specific Aim 3

Aim 3 examines the impact of the intervention on attendance at scheduled dental appointments over the following 12-month period to determine whether the intervention affects avoidance of dental procedures. First, we will examine whether the overall attendance rate is changed from pre- to post-intervention using a one-sample Chisquare test comparing the 12-month periods immediately before and immediately after the delivery of the intervention. The two intervention groups combined will be used for this analysis. We will also use a Chi-square test to compare post-intervention attendance rates between the two intervention groups. We expect the attendance rates will be similar for the two groups. Finally, we will conduct logistic regression analyses predicting attendance/nonattendance among intervention patients who did or did not demonstrate reduction in dental anxiety at 3-month follow-up. Relevant demographic characteristics and other potential confounding variables or moderators will be included in the final logistic models.

Missing Data

MI will be used to handle missing follow-up data when conducting ITT analysis for Specific Aims 1 and 2. There will be three steps in the MI procedure: 1) The missing follow-up data will be filled in 100 times to generate 100 complete datasets; 2) The 100 datasets will be analyzed by analyses of covariance with follow up scores at 1-month or 3-month as outcomes and treatment groups as the independent variable (Tr1 vs. Tr2 for Specific Aim 1, or Tr1 + Tr2 vs. AC for Specific Aim 2), controlling for baseline scores; 3) The results from the 100 complete datasets will be combined for the MI inference (Rubin 1987). SAS PROC MI and PROC MIANALYZE will be used for multiple imputation analysis using SAS 9.4 (SAS Institute Inc., Cary, NC, USA).

Analysis of Secondary Objectives

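### Optional free gain: the screening MDAS is a second pre-randomisation measure of a primary outcome, but no planned model or imputation step names it as a covariate

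*Combined protocol and SAP*

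**What the plan says.** Section 8(a), Recruitment Methods, has the interviewer give the MDAS during the screening call, "which is the primary screening measure of dental anxiety employed in this study". Eligibility depends on that score together with a question on impairment. At Enrollment/Baseline (Time 1) in section 8(c), "Questionnaires specified in Table 1 (Measures and Timing of Their Administration) will also be administered by the interviewer over the phone", and Table 1 marks the MDAS under both the initial screen and the baseline assessment. On timing, "Randomization will be done after the patient has received the consent summary, all baseline assessments are completed", so both scores precede allocation.

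Planned Analyses states: "Primary outcomes will be the MDAS (score ranging from 5 to 25) and the rating of fear of dental procedures from the ADIS-5". For Aims 1 and 2 it specifies linear mixed-effects models for repeated measures, with room for further confounders that are not listed. The Missing Data section analyses each imputed dataset by analysis of covariance at 1 or 3 months, "controlling for baseline scores". It lists no variables for the imputation model. The general covariate rule admits only demographic variables that differ between arms and correlate with outcome. No analysis section mentions the screening MDAS.

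**The concern.** A single five-item score is an imperfect measure of a patient's usual dental anxiety. A second score taken before randomisation carries some further information about the follow-up score, and adjusting for it does not bias a randomised comparison. The plan collects that score, uses it for eligibility, and gives it no stated role afterwards.

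Precision on the MDAS matters most for Aim 1, where two one-sided tests (TOST) are used and the width of the interval helps decide whether equivalence is shown. The plan states no margin, SD or power, so it does not show that precision is to spare. The screening score should also be present for every randomised patient, which makes it a natural auxiliary variable when 1- or 3-month MDAS scores are imputed.

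**Working it through.** **Planned sample size.** The 550 cannot be reproduced: no effect size, SD, equivalence margin, power or dropout allowance is given. The check is therefore limited to how much residual variance the second score removes.

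**Inputs from the protocol.** Test-retest correlation ρ = .82 (MDAS description under Initial Screening Measures); N = 550; selection on the screening MDAS.

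**Assumptions.**
- Scores are normal with unit variance before selection.
- The baseline-to-follow-up correlation r, before selection, is .5, .6 or .7.
- The share p selected on the screen is 10%, 20% or 40%. The Rationale says "Approximately 10-20% of individuals in the US endorse significant dental anxiety", which is a national prevalence and not this clinic's eligible share, so 40% is included as a looser case.
- The screening score's correlation with follow-up is f·r, with f = 1 (as good as baseline), .95 or .90.

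**Step 1: no selection, f = 1.** Residual variance is 1 − r² with one score and 1 − 2r²/(1 + ρ) with two.
- r = .5: .750 to .725, a fall of 3.3%
- r = .6: .640 to .604, a fall of 5.6%
- r = .7: .510 to .462, a fall of 9.5%

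**Step 2: selection on the screen.** Let c be the cut-off, λ = φ(c)/p, and k = 1 + cλ − λ² the variance of the screening score after selection. Then k = .169, .219 and .312 for p = 10%, 20% and 40%. After selection:
- Var(baseline) = 1 − ρ²(1 − k)
- Var(follow-up) = 1 − f²r²(1 − k)
- Cov(baseline, follow-up) = r[1 − ρf(1 − k)]
- Residual with baseline alone: V1 = Var(follow-up) − Cov²/Var(baseline)
- Residual with both: V2 = 1 − r²(1 + f² − 2fρ)/(1 − ρ²), which selection on the screen does not change
- Patient equivalents = 550 × (V1/V2 − 1)

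Example with p = 20%, r = .5, f = 1: Var(baseline) = 1 − .6724 × .7814 = .475; Var(follow-up) = 1 − .25 × .7814 = .805; Cov = .5 × (1 − .82 × .7814) = .180. So V1 = .7367 and V2 = .7253. The fall is 1.5%, and 550 × (.7367/.7253 − 1) is about 9 patients.

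Fall in residual variance (patient equivalents), f = 1:

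| Selected | r = .5 | r = .6 | r = .7 |
|---|---|---|---|
| Top 10% | 1.3% (7) | 2.2% (12) | 3.9% (22) |
| Top 20% | 1.5% (9) | 2.6% (15) | 4.6% (27) |
| Top 40% | 1.9% (11) | 3.3% (19) | 5.7% (34) |

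**Step 3: an earlier score that predicts less well.** Over the same grid, f = .95 gives falls of 0.7% to 2.9% (about 4 to 17 patients), and f = .90 gives 0.3% to 1.1% (about 1 to 6 patients).

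**The case against.** The strongest reply is that nothing here is wrong. Adjusting an outcome for its own baseline value is standard, the documents do not contradict themselves on this point, and a second, overlapping score is a refinement. That stands, and it is why the point is optional.

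Three stronger readings are tempting, and the documents do not support them.

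- *A reader might infer that all the models adjust for the baseline score alone.* Only the analysis of covariance in the Missing Data section says so. The mixed models state no baseline handling and leave other confounders open. Likewise, the screening score is not shown to be excluded from the imputation model, because no imputation variables are listed.
- *A reader might infer a gain of 3-9%, or 18-57 patients.* That follows from correlations of .4-.6 within the enrolled sample and a screening score as predictive as baseline. Under top-10% selection, a pure retest with pre-selection correlation .82 would have an enrolled-sample correlation of only .82 × (1 − .82 × .8309)/(1 − .6724 × .8309) = .59. A value of .6 after an intervention meant to change the score is therefore out of reach in that case, and the upper end of the range is optimistic.
- *A reader might infer a specific rise in equivalence power.* That would need a margin the documents do not give.

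The selection model is also only approximate. Eligibility can be met by 4 or 5 on two of the five items, so a total as low as 4 + 4 + 1 + 1 + 1 = 11 qualifies. Truncation is then less sharp than a single cut on the total. Finally, the benefit as an auxiliary variable for imputation has not been quantified.

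**Conclusion.** The observation holds as an optional, free improvement. Two MDAS scores precede randomisation, the screening score has no named role in any analysis, and the main mixed models leave even the baseline score's role unstated. Under the assumptions above, adding the screening score lowers MDAS residual variance by about 1-6% (roughly 7-34 patient equivalents of 550). The gain drops to about 0.3-3% if the earlier score predicts follow-up 5-10% less well than baseline.

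These figures rest on ρ = .82, assumed values of r and of the selected share, and normality. The protocol gives neither the baseline-to-follow-up correlation nor the screen-to-baseline correlation in this sample. The gain reaches the MDAS only: the ADIS-5 fear rating, the other primary outcome, is not taken at screening and does not benefit directly. Leaving the score out does not bias or invalidate the planned comparisons.

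**What to change.** Before outcomes are analysed by arm, for the MDAS outcome only:

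1. In the Aim 1 and Aim 2 analyses of covariance and mixed models, prespecify both the baseline MDAS and the screening MDAS as covariates, with the follow-up scores as the responses. This also settles how baseline enters the mixed models.
2. Include the screening MDAS in the PROC MI imputation model, and list that model's variables.
3. State that the screening MDAS is not an outcome time point and does not replace baseline in the within-group change analyses. Eligibility truncates it, so change measured from it would include regression to the mean.

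The cost is a few lines of analysis-plan wording and one extra model term, with no new data, visits or patients.

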A more thoroughly detailed version of the consent form used during the initial telephone contact will be given to the patient on his/her arrival for the Time 2 appointment, any further questions will be addressed. Electronic informed consent will be obtained at that time using Adobe Acrobat. An electronically signed copy of the consent form will be provided to the patient via email, and another signed copy will be placed in the patient's research record. The dental anxiety intervention will then be administered (or filler activities will be completed for active control participants). Immediately upon the completion of the intervention and immediately after the completion of the following scheduled dental appointment (Times 2 and 3, respectively), debriefing interviews will be administered. These are described in the section on Study Procedures/Evaluations below.

Follow-up Visits (Times 4 and 5)

Time 4 is the follow-up contact one month (i.e., 4-5 weeks) after the day of the dental anxiety intervention and the scheduled dental appointment. This is the first opportunity for an in-depth follow-up assessment, and the full list of assessments administered at

Page 10 of 28 Revision: May 12, 2023

the pre-intervention assessment session will be re-administered. This includes the ADIS-5 interview, amended to include some debriefing questions as described above, and all questionnaires including the Client Satisfaction Questionnaire (CSQ-8). This session will be scheduled as an in-person visit, with both interview and questionnaires completed in the research offices. However, if logistical barriers or scheduling difficulties arise, the session may be conducted by telephone. In that circumstance, questionnaires may be administered over the phone or online.

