Note: we will modify the instructions for some questionnaires to refer to the present time or the time since the last assessment, depending on when the scale is administered, so that the relevant time interval is examined.

Client Satisfaction Questionnaire (CSQ-8; Larsen et al., 1979). The CSQ-8 is used in the measurement of client/patient assessment of satisfaction with services and clinical care. It consists of 8 items rated on a 1-to-4 scale. Higher scores indicate greater satisfaction with services, with a maximum score of 32. The CSQ-8 will be administered

Page 12 of 28 Revision: May 12, 2023

on treatment day and at the 1-month and 3-month follow-ups to patients who received the online dental anxiety intervention only.

Anxiety Sensitivity Index-3 (ASI-3: Taylor et al., 2007). The ASI-3 is an 18-item measure which assesses the extent to which individuals are concerned about the potential negative consequences of anxiety-related symptoms and sensations. The ASI-3 has demonstrated high internal consistency (α = .95) and convergent validity with a wide range of established anxiety-related measures (Gonzalez et al., 2011). Anxiety sensitivity is significantly correlated with fear of pain, and fear of pain predicts increased pain, expectation of pain, and avoidance of potentially painful experiences (Ocañez et al., 2010). The ASI-3 will be administered at baseline and the 1-month and 3-month follow-ups.

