Post-Appointment Debriefing Ratings. Two separate sets of interview questions will be administered, one after the completion of the dental anxiety intervention and the other after completion of the following dental appointment. The debriefing interview after the dental anxiety intervention will ask the patient to rate the perceived helpfulness of each component of the intervention, the degree to which any of the components were hard to understand, and the degree of difficulty they experienced watching each set of videos of dental procedures. It will also include an open-ended probe of patients' reactions to any aspect of the dental anxiety intervention. These questions will be asked for the purpose of collecting qualitative data on patients' reactions to the intervention, to determine whether there are differences between patients assisted by psychology versus dental staff, and to gather information to inform future modifications of the intervention. Questions will also be asked to determine the degree of pain and the degree of anxiety patients expect to experience in the dental treatment appointment they will have immediately following the dental anxiety intervention. Because this interview will not be administered to patients randomized to the active control condition, the ratings of expected pain and anxiety will be administered to them after they watch the control video.

Ratings after the dental appointment will assess the degree of pain and anxiety experienced during the appointment, the degree of pain and anxiety in comparison to past dental appointments, how much the dental anxiety intervention helped the patient

Page 15 of 28 Revision: May 12, 2023

to get through the dental procedure (for the full intervention and the major components), and the likelihood of scheduling a dental appointment in the future. The debriefing interview after the dental appointment will also include an open-ended probe of patients' thoughts about the impact that any aspect of the dental anxiety intervention may have had on their reactions to the dental procedure. An abbreviated version of this interview will be administered to active control patients, asking about pain and anxiety, and omitting any questions related to the dental anxiety intervention.

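### Outcome ratings share an interview with intervention-evaluation questions in the I-CBT arms but not in controls on treatment day, and undefined debriefing questions are built into the follow-up ADIS-5, so measurement may depend on arm

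*Combined protocol and SAP*

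**What the plan says.** All places are in the combined protocol and SAP, Section 8(c) unless noted.

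- **Treatment day, after the session** (Post-Appointment Debriefing Ratings). The I-CBT interview "will ask the patient to rate the perceived helpfulness of each component of the intervention". It also covers what was hard to follow and how difficult the videos were to watch, and it has an open question on reactions. The text then adds: "Questions will also be asked to determine the degree of pain and the degree of anxiety patients expect to experience" at the appointment about to begin. Controls are handled differently: "Because this interview will not be administered to patients randomized to the active control condition, the ratings of expected pain and anxiety" are collected from them on their own, once the control video has ended.
- **Treatment day, after the appointment** (same section). I-CBT patients report the pain and anxiety they experienced and also "how much the dental anxiety intervention helped the patient" through the procedure. For controls: "An abbreviated version of this interview will be administered to active control patients, asking about pain and anxiety", without the intervention questions. The pain intensity scale (PI-NRS) belongs to this interview.
- **Months 1 and 3** (Follow-up Visits, Times 4 and 5). Both paragraphs say of the session: "This includes the ADIS-5 interview, amended to include some debriefing questions as described above". Planned Analyses names the MDAS and the ADIS-5 fear rating as the primary outcomes.
- **Satisfaction questionnaire (CSQ-8).** Its description has it given "on treatment day and at the 1-month and 3-month follow-ups to patients who received the online dental anxiety intervention only". The follow-up paragraphs list it in the same session with no arm restriction.

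Anticipated and perceived pain and anxiety form a secondary objective (Section 4). No section fixes the order of questions at any of these contacts, and none describes masking of the follow-up interviewers.

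**The concern.** A self-rating can shift with what the patient was asked just before it. A patient who has just told staff how helpful a treatment was may rate their own fear or expected pain to match. One who has just recalled distressing videos may rate it higher. If those questions reach only the I-CBT arms, the comparison with control mixes the effect of treatment with the effect of the interview around the rating.

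The follow-up ADIS-5 raises a second issue. Its fear rating comes from a clinician-administered interview. A question about the intervention placed inside that interview would tell the interviewer which kind of arm the patient was in, possibly before the rating is assigned.

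At stake are the Aim 2 superiority comparison on ADIS-5 fear, on the MDAS if it is asked after evaluative items, and the secondary comparison of anticipated and perceived pain and anxiety. A larger sample would not remove such a shift.

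**Working it through.** The plan gives no figure on this point to reproduce, so the check is mainly a comparison of texts.

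**Step 1. What each arm is asked.**

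| Occasion | I-CBT arms | Control arm | Outcome at stake |
|---|---|---|---|
| Treatment day, after session | Expected pain and anxiety, within an evaluation interview | Expected pain and anxiety alone | Secondary |
| Treatment day, after appointment | Experienced pain and anxiety, plus intervention questions | Pain and anxiety only | Secondary |
| Months 1 and 3, ADIS-5 | Debriefing questions added, content not stated | Not stated | Primary (fear rating) |
| Months 1 and 3, CSQ-8 | Given | Not given, per its own description | Same session as both primary outcomes |

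The difference between arms is explicit in the first two rows. Table 1 schedules neither primary outcome on treatment day, so those rows touch secondary ratings only.

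**Step 2. What the ADIS-5 amendment could contain.** The follow-up paragraphs refer back to a description above them. The preceding paragraph (Intermediate Visits) only mentions debriefing interviews and points ahead to Study Procedures/Evaluations. The sole description there is Post-Appointment Debriefing Ratings. Most of that content evaluates the intervention, and controls cannot answer it as it stands. A few items (pain, anxiety, likelihood of booking again) are neutral. An arm difference in the ADIS-5 is therefore a reasonable inference, not a stated fact.

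**Step 3. Order.** In the first debriefing, evaluation is listed before expected pain and anxiety. In the second, pain and anxiety are listed first. The follow-up paragraphs list the ADIS-5 before the questionnaires, and Table 1 has the MDAS first and the CSQ-8 last. None of these lists is an instruction on order.

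**Step 4. Which contrasts are exposed.** Let b be a shift in reported score common to both I-CBT arms.

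- Aim 1 (psychology versus dental staff): (m1 + b) - (m2 + b) = m1 - m2. The shift cancels.
- Aim 2 (pooled I-CBT versus control): (m + b) - mc = (m - mc) + b. The shift stays in full.

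**Step 5. Illustration of sensitivity, not an estimate.** Inputs: N = 550 in three roughly equal arms (Section 8(a)) and alpha 0.05 (Planned Analyses; two-sided assumed). Assumed: SD = 1, no true effect, and a simple comparison at one time point.

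- Control n = 550/3 = 183.3; pooled I-CBT n = 366.7.
- SE = sqrt(1/183.3 + 1/366.7) = 0.0905 SD.
- Probability of a significant result = 1 - Φ(1.96 - b/SE) + Φ(-1.96 - b/SE).
- For b = 0.10: b/SE = 1.11, giving about 0.20.

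| Assumed shift b (SD) | All 550 | 20% loss per arm (assumed) |
|---|---|---|
| 0 | 0.05 | 0.05 |
| 0.05 | 0.09 | 0.08 |
| 0.10 | 0.20 | 0.17 |
| 0.20 | 0.60 | 0.51 |
| 0.30 | 0.91 | 0.84 |

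The planned baseline-adjusted and mixed models would have a different SE. The probabilities are the same for a shift of either sign. The table shows only that a small shift would matter if it occurred.

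**The case against.** The case against is substantial, and several stronger readings fail on the text.

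- **A reader might infer that controls get a stripped-down ADIS-5.** The documents do not say so. The abbreviated version is the post-appointment debriefing on treatment day. For the ADIS-5, the arm is simply not stated.
- **A reader might infer that evaluation always comes before the outcome.** Listing order is not administration order. Read as if it were, most of the lists would put outcomes first.
- **A reader might infer a bias of known size in favour of I-CBT.** No document supports a size. The treatment-day interview also asks about difficulty and distressing videos, which could raise expected anxiety, so the direction is open too.
- **A reader might infer that the two I-CBT arms are pulled together in Aim 1.** An equal additive shift cancels in that difference.
- **A reader might count three documented occasions.** The arm difference in the interviews holding the outcome ratings is documented only for treatment day.

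Two further points are fair. Some difference is unavoidable, because controls cannot rate an intervention they did not receive, and the core pain and anxiety ratings are kept in every arm. Masking is also a wider question: the coordinator conducts follow-up interviews and rates fidelity for some sessions (Section 6), so the cue adds nothing where the interviewer already knows the arm.

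What survives is that the unavoidable questions need not sit before, or inside, the outcome measurement. Nothing in the plan keeps them out.

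**Conclusion.** The point holds as a risk of arm-dependent measurement. The different context for expected pain and anxiety is explicit. The same holds for experienced pain and anxiety, with weaker exposure because those ratings are listed first. For ADIS-5 fear the risk is an inference from an amendment with no stated content, position or arm. It concerns Aim 2 and the secondary pain and anxiety comparison, not the Aim 1 difference between I-CBT arms, provided any shift is the same in both. The MDAS is exposed only if it follows evaluative items.

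Neither size nor direction can be taken from the documents, and the probabilities above rest wholly on assumed shifts. The change is still worth making: a primary-outcome interview is modified at follow-up without specification, and the remedy is a matter of order.

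**What to change.** Use one order in all three arms.

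1. **After the session or control video:** ask expected pain and expected anxiety first, straight away and in identical words. I-CBT debriefing follows.
2. **After the appointment:** take experienced pain and anxiety, including the PI-NRS, before any question about the intervention.
3. **Months 1 and 3:** complete the MDAS and the unamended ADIS-5 module, with scores entered, before any debriefing question or the CSQ-8. Run debriefing as a separate last form.

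In the Time 4 and Time 5 paragraphs, the clause on the amended ADIS-5 could be replaced by: *The MDAS and the ADIS-5 module, in its baseline form, are completed and scored first. Debriefing questions, listed by arm, and the CSQ-8 where it applies are given afterwards on separate forms.*

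This needs no new items, staff or visits. The main drawback is timing. On the plan's schedule (award August 2018, then 6 + 45 + 3 = 54 months), 3-month assessments would end around February 2023, while this revision is dated May 12, 2023. Unless recruitment ran late, which the documents do not show, few patients would be reached. Patients already assessed keep the order they had, so a change now could mix two orders. Record the order actually used in each arm and the change date, and report any arm difference in order as a limitation.
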